Email Campaign to Encourage Patients to Complete Sign-up Process for Geisinger's Patient Portal

NCT04332614

April 5, 2021

Study Protocol

Purpose

The purpose of the current study was to assess what kind of messaging improves the effectiveness of an email campaign targeted at enrolling patients into Geisinger's online patient portal, called myGeisinger. Currently, Geisinger sends an email every month to patients who have started but not completed the enrollment process (they have had an activation code generated but have not yet used that code to enroll). This study A/B tested 5 email messages to assess if they performed better than the current standard email message.

Background

In order to enroll in the myGeisinger patient portal, an activation code has to first be generated for a patient, which the patient subsequently uses to enroll in the portal. This code can be requested by the patient or generated by healthcare staff. Any patient who has had an activation code generated but has not yet enrolled is assigned a myGeisinger status of "Pending." Every month, patients with this status are sent an email encouraging them to enroll.

Method

Sample

The study population consisted of patients aged 18-88 who had an email address on file, a myGeisinger status of "Pending", and had not received emails from this monthly myGeisinger marketing campaign within the last 2 months. These eligibility criteria were used to match the ongoing marketing campaign already in place.

Based on the above criteria, N = 14,099 patients were randomized to a study condition and sent an email on April 6, 2020. Electronic Health Records for these patients were subsequently examined ~1 week and ~1 month after the campaign. We were only able to match unique records for 13,523 patients after ~1 week and for 13,344 patients after ~1 month, which served as the final sample for those respective analyses.

Intervention

Patients were randomly assigned to receive one of six emails. Each email intervention is named and described in the pre-registration under "Groups and Interventions." The precise email content is included in the Appendix below.

Outcomes

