As described in the "Outcome Measures" section of the pre-registration, three outcome measures were assessed: Email opened, Link clicked, and Enrollment. The main purpose of examining *Email opened* was to evaluate the impact of the subject line; therefore, all patients whose emails were not delivered (i.e. bounced) were excluded from this analysis. The main purpose of *Link clicked* and *Enrollment* was to evaluate the impact of the full email (subject line and body); therefore, these outcomes were only assessed among patients who opened the email.

Data Extraction

The goal of this study was to evaluate outcome measures both 1 week and 1 month after the launch of the intervention. Technical issues resulted in delays in these data extractions. In addition, Enrollment data resided in a different database than the remaining email engagement data and was therefore extracted separately and subject to different delays. Below is the exact timeline of data extraction:

04/14/20 [08 days post-launch]: “1-week” engagement data

04/16/20 [10 days post-launch]: “1-week” enrollment data

05/08/20 [32 days post-launch]: “1-month” enrollment data

05/11/20 [35 days post-launch]: “1-month” engagement data

Statistical Analysis Plan

The primary questions of interest were whether each of the high-level interventions – less-is-better, social proof, or endowment – performed better than the standard email, which served as the control group. This was evaluated for all three outcome measures using a logistic regression (a generalized linear model with a binary distribution and log-link function) with the Standard Email condition dummy coded as the reference level. This dummy coding allowed for the comparison of each high-level intervention vs. control within a single model.

A secondary question of interest was: which less-is-better condition – provider communication, managing appointments, or medical information access – performed best? This was evaluated for all three outcome measures using a logistic regression (a generalized linear model with a binary distribution and log-link function). Each pair-wise comparison was evaluated with the appropriate correction for multiple corrections using a Tukey's test.

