For both evaluations described above, a primary analysis was conducted for the outcome approximately 1 week after the intervention, and a secondary analysis was conducted approximately 1 month after the intervention. See the *Data Extraction* section of the *Study Protocol* above for the exact time frame.

For all tests, odds ratios (ORs) were calculated, along with 95% confidence intervals (CIs); two-tailed p-values < 0.05 were used to determine statistical significance.

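### No outcome hierarchy is stated: the primary question is tested on opens, clicks and enrollment alike, so a claim of better performance could rest on opens alone although the campaign targets enrollment

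*Combined protocol and SAP*

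**What the plan says.** The Purpose section ties effectiveness to one end: messaging that "improves the effectiveness of an email campaign targeted at enrolling patients into Geisinger's online patient portal". The same section then states the test without naming an outcome: "This study A/B tested 5 email messages to assess if they performed better than the current standard email message".

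The Outcomes section lists the measures without order: "three outcome measures were assessed: Email opened, Link clicked, and Enrollment". It refers to the pre-registration for their description and gives them different roles. On opens it says: "The main purpose of examining *Email opened* was to evaluate the impact of the subject line". Clicks and enrollment are there to judge the whole email, and both are analysed only in patients who opened it.

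In the Statistical Analysis Plan, "The primary questions of interest were whether each of the high-level interventions" (less-is-better, social proof, endowment) beat the standard email. On how this is answered: "This was evaluated for all three outcome measures using a logistic regression". The secondary question, which less-is-better email did best, is also put to all three outcomes. Time points are ranked: "a primary analysis was conducted for the outcome approximately 1 week after the intervention", with the 1-month analysis secondary. Every test uses two-tailed p < 0.05. The only multiplicity correction is Tukey's, for the less-is-better pairs.

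**The concern.** The plan ranks its questions (high-level contrasts above less-is-better pairs) and its time points (1 week above 1 month), but not its outcomes. Opening and clicking are steps on the way to enrolling. By the plan's own account, opening mainly reflects the subject line. Yet opens answer the primary question on the same terms as enrollment.

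Two things are at stake. First, a report could say that an intervention outperformed the standard email on the strength of opens, with no evidence that more patients enrolled. The choice of best less-is-better email has the same gap, because the three outcomes may favour different emails and no rule says which one decides. Second, each intervention has three chances to reach significance, so the nominal 5% is not the error rate of a general claim that it did better.

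**Working it through.** The documents give no sample-size calculation, power or familywise error rate, so there is no stated figure to reproduce. The structure comes from the text. The sizes below illustrate it and rest on stated assumptions.

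**Inputs from the documents.** Three high-level contrasts with the standard email; three outcomes; a two-sided 0.05 level for each test; the 1-week analysis primary; no adjustment across outcomes or across the primary contrasts.

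**Number of primary tests.** 3 contrasts x 3 outcomes = 9 at about 1 week.

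**Assumptions for the error rates.** The intervention has no effect on anything. The opens test is independent of the other two; this is reasonable under no effect, because the tests among openers keep their null distribution however many patients open. The click and enrollment test statistics are bivariate normal with correlation r, which the documents do not give and which is varied from 0 to 0.8.

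**One intervention, significance in either direction.** Let N(r) be the probability that neither the click nor the enrollment test has |z| > 1.96. The chance of at least one significant outcome is 1 - 0.95 x N(r).

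- r = 0: N = 0.9025; 1 - 0.95 x 0.9025 = 0.143
- r = 0.3: N = 0.9049; result 0.140
- r = 0.6: N = 0.9125; result 0.133
- r = 0.8: N = 0.9219; result 0.124

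With a single outcome the figure is 0.05.

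**One intervention, false result in its favour only.** Let B(r) be the probability that neither the click nor the enrollment test has z > 1.96. The chance is 1 - 0.975 x B(r).

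- r = 0: B = 0.9506; 1 - 0.975 x 0.9506 = 0.073
- r = 0.8: B = 0.9610; 1 - 0.975 x 0.9610 = 0.063

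With a single outcome the figure is 0.025. In both versions the inflation is about 2.5- to 2.9-fold.

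**False win on opens alone, one intervention.** The chance of being significantly better on opens with neither click nor enrollment significant is 0.025 x N(r) = 0.025 x 0.9025 to 0.025 x 0.9219, or about 0.023.

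**All nine tests, either direction.** If independent, 1 - 0.95^9 = 0.370. The allocation ratio is not stated. A simulation that allowed for the shared control and took r from 0 to 0.9 gave about 0.26-0.32 with six equal arms (less-is-better pooling three) and 0.28-0.33 with four equal groups.

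**After naming one primary outcome.** Nine tests become three. The chance of at least one false significant result is 1 - 0.95^3 = 0.143 if independent, and about 0.12-0.13 with the shared control in the same simulations. It stays above 0.05.

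**Why the enrollment denominator matters.** An example with assumed rates: the standard email is opened by 20%, and 10% of openers enroll, so 0.20 x 0.10 = 2.0% of recipients enroll. A new email is opened by 25%, and 9% of openers enroll, so 0.25 x 0.09 = 2.25% enroll. The new email enrolls more people but looks worse among openers. A rule that made the planned openers-only enrollment analysis decisive could therefore point the wrong way.

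**The case against.** The strongest reply is that the plan never says one significant outcome is enough. It sets a threshold per test and gives each outcome its own purpose, so the natural reading may be three separate answers: one on the subject line and two on the full email. On that reading, a best email that differs by outcome is no contradiction. This stands in part. A reader might infer an explicit any-one-outcome rule, or deliberate equal weighting, but the text contains neither; both would be inferences from silence. A reader might also infer that opens reflect the subject line alone, whereas the plan says that is their main purpose. What remains is that the primary question is framed as better performance, is put to all three outcomes, and carries no condition involving enrollment.

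Second, the pre-registration, to which the plan refers for its outcomes, may rank them. It is not available here, so the point is limited to what this document states. If a ranking exists, it should be repeated in the plan.

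Third, a 12.4-14.3% chance of a false claim of benefit would be too high a figure, because that range counts harm as well as benefit. The favourable direction alone is 6.3-7.3%.

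Fourth, the document is dated April 5, 2021, and the last extraction was on 05/11/20. A hierarchy added now is not prespecification. That is correct, and it affects how the change must be labelled.

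**Conclusion.** The point holds as a missing hierarchy. The document's stated target is enrollment, yet it tests its primary question nine times at an unadjusted two-sided 0.05 and does not stop a claim of better performance from resting on opens. For one intervention without effect, the chance of some significant outcome is about 12.4-14.3% instead of 5%, and of a false favourable one about 6.3-7.3% instead of 2.5%. These sizes depend on opens being independent and on a click-enrollment correlation of 0 to 0.8. The structural finding depends on neither.

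The 0.05 level is not wrong for any single test, and the documents do not show that a claim based on opens alone was made. This should be changed because the remedy is cheap and follows from the sponsor's own stated purpose.

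**What to change.** - Make Enrollment at about 1 week the single primary outcome for the three high-level contrasts, and the outcome on which the best less-is-better email is named.
- Analyse it among all randomized patients with matched records (13,523 of 14,099 at about 1 week), or among all with delivered emails. Do not restrict it to openers, because the email itself affects who opens.
- Report opens, clicks and enrollment among openers as secondary engagement results, and word an effect seen only on opens or clicks as an engagement effect.
- If the pre-registration ranks the outcomes, repeat that ranking. Otherwise label the hierarchy as set after data extraction.
- State that the three unadjusted contrasts with the shared control still carry a familywise error above 5% (up to 14.3% if independent).

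**Cost.** All planned models still run. The additions are an enrollment analysis in the wider population, revised wording, and the post hoc label if it applies. Opens and clicks lose primary status, enrollment among all recipients is a lower rate than among openers, and the headline may be less favourable.

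### Does the log link named beside logistic regression leave the effect measure in doubt?

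*Combined protocol and SAP*

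**What the plan says.** The Statistical Analysis Plan section defines two models. For the primary question, each high-level intervention is compared with the standard email by "a logistic regression (a generalized linear model with a binary distribution and log-link function) with the Standard Email condition dummy coded" as the reference. For the secondary question, the three less-is-better emails are compared with one another "using a logistic regression (a generalized linear model with a binary distribution and log-link function). Each pair-wise comparison was evaluated", with a Tukey adjustment. The parenthesis is the same in both places.

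The closing paragraph of the section fixes the effect measure and the decision rule for all tests: "odds ratios (ORs) were calculated, along with 95% confidence intervals (CIs"), and "two-tailed p-values < 0.05 were used to determine statistical significance".

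Condition is the only predictor that either model description names. The three outcomes (email opened, link clicked, enrollment) are all binary. The document gives no outcome rates, arm sizes or allocation ratio.

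**The concern.** One sentence gives the model a name that implies one link and a parenthesis that states another. A binomial model with a logit link has exponentiated coefficients that are odds ratios. With a log link (the log-binomial model) they are risk ratios. An analyst who followed the parenthesis literally, exponentiated the coefficients and labelled the results odds ratios would report a mislabelled effect.

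The parenthesis is also the only technical definition of the model. It covers three outcomes, two time points and both questions, so a wrong link would affect every ratio reported. The word logit appears nowhere, and the document does not say how an odds ratio would be obtained from a log-link fit. For a common outcome, which email opening may be, the two ratios can differ appreciably.

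**Working it through.** **What the text itself indicates.** Three statements bear on the link.

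| Statement | Link implied |
|---|---|
| Model name, given for both models | logit |
| Parenthesis, same wording for both models | log |
| Effect measure for all tests: odds ratio | logit |

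No risk ratio, relative risk or log-binomial model is mentioned. The second parenthesis repeats the first, so it is not separate evidence for a log link.

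**What would change if a log link had been used.** The plan gives no figure to reproduce, so the rates below are assumptions.

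Inputs:
- 1-week sample of 13,523 (Method, Sample: "We were only able to match unique records for 13,523 patients after ~1 week").
- Six emails (Method, Intervention: "Patients were randomly assigned to receive one of six emails").
- Assumed equal allocation: 13,523 / 6 = 2,253.8, taken as n = 2,254 per email, ignoring bounced emails.
- Pooled less-is-better: 3 × 2,254 = 6,762.
- Openers per email if 30% open (assumed): 0.30 × 2,254 = 676.

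Formulas, with p0 and p1 the event proportions in the standard and intervention groups and event counts rounded to whole patients:
- Log link: RR = p1/p0; SE(ln RR) = √[(1−p0)/(n0·p0) + (1−p1)/(n1·p1)].
- Logit link: OR = [p1/(1−p1)] / [p0/(1−p0)]; SE(ln OR) = √[1/(n0·p0(1−p0)) + 1/(n1·p1(1−p1))].
- 95% CI = exp(estimate ± 1.96·SE); two-sided Wald p from estimate/SE.

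Worked example, 30% vs 35% (676 and 789 events out of 2,254 each):
- ln RR = 0.1546, SE = 0.0431, so RR = 1.17 (1.07–1.27), p = 0.00034.
- ln OR = 0.2289, SE = 0.0637, so OR = 1.26 (1.11–1.42), p = 0.00033.

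| Assumed comparison | Log link: RR (95% CI) | Logit link: OR (95% CI) | p, log / logit |
|---|---|---|---|
| Opened, 10% vs 12% | 1.20 (1.02–1.42) | 1.23 (1.02–1.48) | 0.0324 / 0.0323 |
| Opened, 30% vs 35% | 1.17 (1.07–1.27) | 1.26 (1.11–1.42) | 0.00034 / 0.00033 |
| Opened, 50% vs 53% | 1.06 (1.00–1.12) | 1.13 (1.00–1.27) | 0.0428 / 0.0427 |
| Opened, 50% vs 60% | 1.20 (1.14–1.27) | 1.50 (1.33–1.69) | both far below 0.001 |
| Opened, pooled less-is-better (6,762) vs standard, 30% vs 33% | 1.10 (1.02–1.18) | 1.15 (1.04–1.27) | 0.0091 / 0.0083 |
| Enrolled among openers (676 each), 5% vs 6% | 1.21 (0.78–1.88) | 1.22 (0.76–1.95) | 0.406 / 0.406 |

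**Check on the four-group primary model.** Binomial models were fitted with each link at assumed rates of 30% (standard), 33% (less-is-better), 35% (social proof) and 32% (endowment). Both links gave the same fitted probabilities: 0.2999, 0.3299, 0.3500 and 0.3199. For the three contrasts with standard:
- Exponentiated coefficients: 1.100, 1.167 and 1.067 under log; 1.149, 1.257 and 1.098 under logit.
- p-values: 0.0091, 0.00034 and 0.1474 under log; 0.0083, 0.00033 and 0.1473 under logit.

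A model holding only condition indicators has one parameter per group, so it reproduces the group proportions whatever the link. The link sets the scale of the ratio and hardly touches the test.

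**The case for a change.** The strongest case for acting is that a likely reading is not a confirmed one. The phrase occurs twice, so it could be reused boilerplate or could reflect the code. The stated odds ratio supports logit without proving it, because an exponentiated log-link coefficient could have been mislabelled. Only the code settles the matter, the check is cheap, and a specification should not admit two models.

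Much of this stands. The parenthesis is wrong as written, PDF conversion does not explain it, and the document cannot prove what was run. What does not stand is the step to a consequence for this trial. The plan says outright that the ratios are odds ratios. An odds ratio can also be recovered from the fitted probabilities of a log-link model, so even a log link would not by itself falsify that statement. A wrong result requires both that a log link was fitted and that its coefficients were labelled odds ratios, and nothing in the document shows either. The document is also retrospective: it is dated April 5, 2021, and the last data extraction was on 05/11/20. Rewording it cannot alter how the analysis was done.

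**Conclusion.** The log link is a slip for logit, and a competent analyst would read it so from the model name and the effect measure. Correcting the word would tidy the text without changing what the trial does or concludes, so no change to the plan is called for.

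On the size of the issue: in the comparisons checked, p-values differ by at most 0.0008 (0.0091 against 0.0083) and none changes side at 0.05. Only a p-value already sitting almost on the threshold could do so. The ratio itself would differ negligibly for a rare outcome (1.21 against 1.22) and noticeably for a common one (1.20 against 1.50), but only in the undocumented case of a log-link estimate reported as an odds ratio.

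This rests on three assumptions: the illustrative rates and equal arm sizes, since the document gives none; condition being the only predictor, which the plan implies but does not state; and the model name and effect measure being better evidence of what was fitted than the parenthesis.

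### The planned logistic models name no covariate besides email condition, although age was known for every randomized patient; if age predicts the outcomes, adjusting for it would give a small gain in power

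*Combined protocol and SAP*

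**What the plan says.** The Statistical Analysis Plan describes two models. The first compares the high-level interventions with control for all three outcomes, "with the Standard Email condition dummy coded as the reference level". The second compares the three less-is-better emails with one another: "Each pair-wise comparison was evaluated with the appropriate correction for multiple corrections using a Tukey's test". Neither description names a baseline covariate. Results are odds ratios with 95% confidence intervals, tested two-sided at 0.05.

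Under Method, Sample: "The study population consisted of patients aged 18-88 who had an email address on file". Eligibility therefore required each patient's age before the email. The Background adds of the activation code: "This code can be requested by the patient or generated by healthcare staff". It does not say that the route was stored or extracted for each patient.

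On numbers, "N = 14,099 patients were randomized to a study condition and sent an email on April 6, 2020", and records were matched for "13,523 patients after ~1 week and for 13,344 patients after ~1 month". Under Outcomes, Email opened excludes bounced emails, and Link clicked and Enrollment are assessed only among patients who opened the email. No outcome rate, power, precision target or covariate association is given.

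**The concern.** Age covers a 70-year span and could well be related to how patients respond to an email about an online portal. A variable fixed before randomization that predicts the outcome can be used to sharpen a randomized comparison at no cost in patients. If it is left out, the variation it explains stays in the noise. At stake is a modest amount of power in each email comparison, together with an estimate that takes account of any chance age difference between the six arms. The validity of the unadjusted test is not in question.

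**Working it through.** The plan states no power or precision figure, so there is nothing of its own to reproduce. The check asks how much age alone could contribute.

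**Inputs from the documents.** Age range 18-88; 13,523 patients matched at about 1 week; six emails ("Patients were randomly assigned to receive one of six emails"); two-sided 0.05; odds ratio as the effect measure.

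**Assumptions, not in the documents.** Outcome rate p of 5%, 20% or 30%. Odds ratio per 10 years of age of 1.2 or 1.4. Age either uniform on 18-88 (SD = 70/√12 = 20.2 years) or normal with SD 15. Equal allocation, giving 13,523/6 = about 2,254 per arm. A conditional email odds ratio of 1.25 for the power figures.

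**Step 1: share of outcome variance explained by age.** R² = Var(E[Y|age]) / (p(1−p)). The equivalent gain in sample size for a standardized marginal estimate is about 1/(1−R²) − 1. This share does not depend on the number of patients, so the missing counts of openers and delivered emails do not alter it.

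| Outcome rate | OR per 10 years | SD 20.2: R², gain | SD 15: R², gain |
|---|---|---|---|
| 5% | 1.2 | 0.0063, 0.6% | 0.0036, 0.4% |
| 5% | 1.4 | 0.0200, 2.0% | 0.0130, 1.3% |
| 20% | 1.2 | 0.0210, 2.1% | 0.0118, 1.2% |
| 20% | 1.4 | 0.0660, 7.1% | 0.0391, 4.1% |
| 30% | 1.2 | 0.0274, 2.8% | 0.0153, 1.6% |
| 30% | 1.4 | 0.0859, 9.4% | 0.0492, 5.2% |

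Example: 1/(1 − 0.0660) − 1 = 0.071. With an odds ratio of 1 for age, R² and the gain are zero.

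**Step 2: what happens to the interval and the power.** Take one email against Standard Email, a 20% control rate, an odds ratio of 1.4 per 10 years and SD 20.2. Averaged over age, the conditional odds ratio of 1.25 becomes a marginal odds ratio of 1.23 (log 0.207).

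- Unadjusted: SE = √[1/(n·p₀(1−p₀)) + 1/(n·p₁(1−p₁))] = 0.0724. Power = Φ(0.207/0.0724 − 1.96), about 82%.
- Age in the model, conditional odds ratio: SE from the logistic information matrix = 0.0751, which is 3.7% larger. Power = Φ(0.2231/0.0751 − 1.96), about 84%.
- Age in the model, predictions standardized to a marginal odds ratio: SE from the efficient influence function = 0.0698, which is 3.6% smaller. Power = Φ(0.207/0.0698 − 1.96), about 84%.

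Over the whole table the power gain is 0.1 to 2.6 points. The standardized SE falls by 0.2% to 4.5%, and the conditional SE rises by 0.2% to 4.7%. The power figures assume 2,254 per arm, which is more than any of the three outcomes would use after the stated exclusions.

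**The case against.** An unadjusted comparison of randomized arms is valid, and leaving out covariates is a legitimate choice. At about 2,254 per arm the SE of a standardized baseline difference is only √(2/2,254) = 0.03 SD, and the unadjusted test already allows for such chance differences. Every figure for the gain rests on assumed associations. All of this stands, and it is why the point is about efficiency only.

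Two stronger readings are tempting, and the documents support neither.

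- A reader might infer that the route of the activation code was also available. The Background says only that two routes exist. Gains that depend on route therefore cannot be counted.
- A reader might infer that every comparison as reported is less precise than it could be, so that adding covariates would narrow the intervals. For the odds ratio taken directly from a logistic model the reverse holds: its SE is unchanged or rises, and it becomes a conditional rather than a marginal quantity. Power can still rise, because the conditional odds ratio lies further from 1. The interval narrows only for a standardized marginal estimate, and only if the covariate is prognostic.

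Two further limits stand. Link clicked and Enrollment use a set chosen after randomization, which the subject line may itself affect; adjusting for age does not restore that comparison. And the document is dated April 5, 2021, while the last extraction under Data Extraction was May 11, 2020. Making an adjusted model the main analysis at that point would add analytic freedom after the data were in.

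**Conclusion.** The point holds as an efficiency improvement. No covariate is named, age was in hand for every randomized patient, and a standardized age-adjusted analysis could add a little power. Under the assumed range, age alone is worth about 1-9% in effective sample size at a 20-30% outcome and 0.4-2% at 5%; it is worth nothing if age does not predict the outcome. The benefit is cleanest for Email opened, where the unadjusted test is valid but may be less efficient. For Link clicked and Enrollment the restriction to openers is a separate problem that this change leaves untouched.

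The calculation takes the model as a logit model because odds ratios are reported. The plan's wording, "logistic regression (a generalized linear model with a binary distribution and log-link function", does not fit that: a true log link would give a risk ratio, and the contrast between conditional and marginal odds ratios would not apply in the same way.

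**What to change.** Add age, as linear plus quadratic terms or a spline, to the primary and secondary logistic models. Standardize the predicted probabilities over the analysed patients and report the resulting marginal odds ratio with its 95% CI next to the unadjusted one, so that both estimate the same quantity. Label the adjusted result supplementary if it was not prespecified before the data were extracted. Add the code route only if the patient record turns out to hold it. Reconcile the stated link function with the odds ratios in the same edit. Do not present the adjustment as a remedy for the openers-only analyses.

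The cost is SAP wording, one field that eligibility already required, and a rerun of the models. No further patients are needed.
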